12.4 Data Management and Coding

The CRO will be responsible for activities associated with the data management of this study. This will include setting up a relevant database and data transfer mechanisms, along with appropriate validation of data and resolution of queries. Data generated within this clinical study will be handled according to the relevant SOPs of the data management and biostatistics departments of the CRO.

Study sites will enter data directly into an electronic data capture system by completing the eCRF via a secure internet connection. Data entered into the eCRF must be verifiable against source documents at the study site. Data to be recorded directly on the eCRF will be identified and the eCRF will be considered the source document. Any changes to the data entered into the electronic data capture system will be recorded in the audit trail and will be United States Food and Drug Administration (FDA) CFR 21 Part 11 compliant. The CRO will provide sites with instructions and a video link for training purposes.

Medical coding will use MedDRA for concomitant diseases and AEs and the World Health Organization Drug Dictionary for medications.

Missing or inconsistent data will be queried via an electronic query raised in the clinical database to the Investigator for clarification. Subsequent modifications to the data will be made by the site directly in the clinical database.

The participants will be identified by a unique trial specific number code in the database. The name and any other identifying detail will NOT be included in any trial data electronic file.

The Investigator and study site staff will ensure that data collected on each subject is recorded in the eCRF as accurately and completely as possible. All appropriate laboratory data, summary reports and Investigator observations will be entered into the eCRF from the relevant source data held in the site medical record(s). It is important to ensure that:

- The relevant eCRFs are completed in a timely fashion.
- All eCRF data are verifiable in the source documentation or the discrepancies must be explained.
- eCRF sections are completed in a timely fashion, as close to the visit or event being recorded as possible.
- Data queries are resolved and documented by authorized study staff. The reason for the change or correction should be given where appropriate.
- As much data as possible is entered and cleaned in preparation for each study database lock point.

The above considerations also apply to subjects who are withdrawn early. If a subject withdraws from the study, the reason must be noted on the appropriate form and the subject must be followed up as per protocol.

12.5 Clinical Study Report

All clinical data will be presented at the end of the study as data listings. These will be monitored to confirm the lists accurately represent the data collected during the course of the study. The trial data will then be locked and a final data listing produced. The Clinical Study Report will be based on the final data listings. The locked trial data may then be used for analysis and publication.

13 RECORDS AND SUPPLIES

13.1 Drug Accountability

On receipt of the study drug, the Investigator (or designee) will conduct an inventory of the supplies and verify that study drug supplies are received intact and in the correct amounts before completing a supplies receipt. The Investigator will retain a copy of this receipt at the study site and return the original receipt to the study monitor. The monitor may check the study supplies at each study site at any time during the study.

The RGT100-PEI finished drug product should be stored safely, in a lockable location frozen at -20°C (±5°C) in an upright position. The vials should be at room temperature at the time of injection. The vials of RGT100-PEI are for single use only and any unused dispersion should remain in the used vial for drug accountability purposes.

It is the responsibility of the study monitor to ensure that the Investigator (or designee) has correctly documented the amount of the study drug received, dispensed, and returned on the dispensing log that will be provided. A full drug accountability log will be maintained at the study site at all times. The study monitor will perform a final inventory of study drug and final drug accountability check at least before closure of the study site. All discrepancies must be accounted for and documented.

The destruction of used and partially used vials will be undertaken at the site according to local hospital policy. The procedure for destruction of unused vials should be adequate and typically via incineration

13.2 Financing and Insurance

13.2.1 Sponsorship

The Sponsor will provide written confirmation of Sponsorship and authorize the trial commencement once satisfied that all arrangements and approvals for the proper conduct of the trial are in place.

13.2.2 Indemnity

Insurance of this study will be outlined in a separate agreement between CRO and the Sponsor.

13.2.3 Contracts/Agreements

This trial is subject to the Sponsor's policy requiring that written contracts/agreements are agreed formally by the participating bodies as appropriate. A Clinical Trial Agreement will be placed between the Sponsor or CRO on behalf of the Sponsor and the participating organizations before site activation. The Sponsor or CRO on behalf of the Sponsor will also set up written agreements with any other external third parties involved in the conduct of the trial as appropriate.

Each participating site will follow local regulations and policy on reimbursement of travel expenses of subjects.

14 ETHICS

14.1 Independent Ethics Committee

Before initiation of the study at each study site, the protocol, subject information sheet, consent form and any other information that will be presented to potential trial subjects (e.g., advertisements or information that supports or supplements the informed consent) will be reviewed and approved by an appropriately constituted REC. Principal Investigators will be approved by the REC. Written approval of the study and all relevant study information must be obtained before the study site can be initiated or the study drug is released to the Investigator. Any necessary extensions or renewals of REC approval must be obtained for changes to the study such as amendments to the protocol, the subject information sheet and consent form or other study documentation. The written approval of the REC together with the approved subject information sheet and consent form must be filed in the study files on site.

The Investigator will report promptly to the REC any new information that may adversely affect the safety of the subjects or the conduct of the study as required. The Investigator will submit written summaries of the study status to the REC as required. On completion of the study, the REC will be notified that the study has ended.

14.2 Regulatory Authorities

Relevant study documentation will be submitted to the regulatory authorities of the participating countries and local authorities as required, according to local/national requirements, for review and approval before the beginning of the study. On completion of the study, the regulatory authorities will be notified that the study has ended.

14.3 Ethical Conduct of the Study

The Investigator(s) and all parties involved in this study should conduct the study in adherence to the ethical principles based on the Declaration of Helsinki, GCP, ICH guidelines, and the applicable national and local laws and regulatory requirements.

14.4 Local Research Governance

Investigators are responsible for ensuring they obtain local management agreement to conduct the trial in accordance with local arrangements and policies.

14.5 Informed Consent

The Investigator is responsible for ensuring that no subject undergoes any study-related examination or activity before that subject has given written informed consent to participate in the study.

Potential participants will be given a current, approved version of the subject information sheet and consent form. They will also receive clear verbal information about the study detailing no less than: the nature of the study; the implications and constraints of the protocol; the known side effects and any risks involved in taking part. It will be explained that they will be free to withdraw from the study at any time, for any reason, without prejudice to future care, and with no obligation to give a reason for withdrawal. They will have sufficient time to

consider the information provided and the opportunity to question the Investigator, their GP or other independent parties before deciding whether to participate.

The Investigator who obtains consent must be suitably qualified and experienced. All delegates must be authorized by the Principal Investigator to obtain consent. The Investigator is responsible for ensuring that the trial consent procedures comply with current applicable GCP, regulatory and ethical requirements. Informed consent discussions and outcomes must be well documented in the medical record. The Investigator must be satisfied that the subject has made an informed decision before taking consent. The subject and the Investigator must personally sign and date the current approved version of the informed consent form according to the sites respective countries regulations. A copy of the information and signed consent form will be given to the participant. The original signed form will be retained at the trial site, with copies held in both the medical record and Investigator Site File (ideally the original if local policy permits).

If new information becomes available that may be relevant to the subject's willingness to continue participation in the study, a new subject information sheet and consent form will be approved by the REC (and regulatory authorities, if required). The study subjects will be informed about this new information and re-consent will be obtained.

Contraceptive/pregnancy counselling

All participants must be advised on the need to use reliable methods of contraception during the study. The advice should include:

1. The acceptable methods, including: male or female sterilization, implants, injectable, combined oral contraceptives, some intrauterine devices, and abstinence (i.e., refraining from heterosexual intercourse for the entire period of risk [during treatment and for 6 months after]). Periodic abstinence is not acceptable (calendar, symptothermal, post-ovulation methods), nor is the withdrawal method (coitus interruptus). The reliability of sexual abstinence needs to be evaluated in relation to the duration of the clinical trial and the preferred and usual lifestyle of the subject.
2. The recommendation that a barrier method should be used in addition to another form of contraception.
3. Males and females should continue to take these precautions for a minimum 6 months after the last dose of study drug.
4. That any pregnancy (also applies to females partners of male trial subjects) occurring within 6 months of the last administration of study drug will be followed up and the outcome of all pregnancies (spontaneous miscarriage, elective termination, normal birth or congenital abnormality) will be reported and followed up even if the participant is discontinued from the study.

14.6 Subject Confidentiality

Personal data recorded on all documents will be regarded as confidential, and to preserve each subject's anonymity, only their initials and date of birth will be recorded on the eCRFs.

The Investigator site must maintain the subject's anonymity in all communications and reports related to the research. The Investigator site team must keep a separate log of enrolled subjects' personal identification details as necessary to enable them to be tracked. These documents must be retained securely, in strict confidence. They form part of the Investigator Site File and are not to be released externally.

Monitors, auditors, and other authorized agents of the Sponsor and/or its designee, the REC(s) approving this research, regulatory authorities, as well as that of any other applicable agencies, will be granted direct access to the study subjects' original medical records for verification of clinical study procedures and/or data, without violating the confidentiality of the subjects to the extent permitted by the law and regulations. In any presentations of the results of this study or in publications, the subjects' identity will remain confidential.

14.7 Protocol Amendments

Amendments are changes made to the research following initial approval. A 'substantial amendment' is an amendment to the terms of the responsible authority application (if applicable), the REC application, or to the protocol or any other supporting documentation, that is likely to affect to a significant degree:

- The safety or physical or mental integrity of the subjects of the trial;
- The scientific value of the trial;
- The conduct or management of the trial; or
- The quality or safety of the investigational medicinal product(s) used in the trial.

Non-substantial amendments are those where the change(s) involve only minor logistical or administrative aspects of the study.

All amendments will be generated and managed according to the CRO's SOPs to ensure compliance with applicable regulations and other requirements. Written confirmation of all applicable REC, regulatory and local approvals must be in place before implementation by Investigators. The only exceptions are for changes necessary to eliminate an immediate hazard to study subjects (see below).

It is the Investigator's responsibility to update subjects (or their authorized representatives, if applicable) whenever new information (in nature or severity) becomes available that might affect the subject's willingness to continue in the trial. The Investigator must ensure this is documented in the subject's medical notes and the subject is re-consented if appropriate.

14.8 Urgent Safety Measures

The Sponsor or Investigator may take appropriate urgent safety measures to protect trial participants from any immediate hazard to their health or safety. Urgent safety measures may be taken without prior authorization. The trial may continue with the urgent safety measures in place. The Investigator must inform the CRO and / or Sponsor immediately if the study site initiates an urgent safety measure:

The notification must include:

- Date of the urgent safety measure;
- Who took the decision; and
- Why the action was taken.

The Investigator will provide any other information that may be required to enable the CRO to report and manage the urgent safety measure in accordance with the current regulatory and ethical requirements for expedited reporting and close out. The CRO will follow written procedures to implement the changes accordingly.

14.9 Temporary Halt

The Sponsor and Investigators reserve the right to place recruitment to this protocol on hold for short periods for administrative reasons or to declare a temporary halt. A temporary halt is defined as a formal decision to:

- Interrupt the treatment of subjects already in the trial for safety reasons;
- Stop recruitment on safety grounds; or
- Stop recruitment for any other reason(s) considered to meet the substantial amendment criteria, including possible impact on the feasibility of completing the trial in a timely manner.

The CRO will report the temporary halt via an expedited substantial amendment procedure to authorities as required. The trial may not restart after a temporary halt until a further substantial amendment to re-open is in place. If it is decided not to restart the trial this will be reported to authorities as an early termination as required.

14.9.1 Serious Breaches

The CRO and/or the Sponsor should notify any "serious breaches" to the appropriate authorities within 7 days of CRO and/or the Sponsor becoming aware of the breach. A serious breach is defined as "A breach of GCP or the trial protocol which is likely to effect to a significant degree:

- the safety or physical or mental integrity of the subjects of the trial; or
- the scientific value of the trial"

Investigators must notify the CRO upon awareness within 1 working day if any serious breach of GCP is suspected. The CRO will review the event and, if appropriate will report a serious breach to all required agencies and authorities within 7 days of the CRO becoming aware of the breach or sooner as required by local regulation.

14.9.2 Trial Reports

Where appropriate, the CRO will be asked to submit Development Safety Update Reports.

This protocol will comply with all current applicable Regulatory Authority, Ethics Committee, and Sponsor reporting requirements.

The CRO will determine which reports need to be circulated to Principal Investigators and other interested parties. Study sites are responsible for forwarding trial reports they receive to their local organizations as required.

15 REPORTING AND PUBLICATION, INCLUDING ARCHIVING

During the clinical trial and after trial closure the Investigator must maintain adequate and accurate records to enable the conduct of the clinical trial and the quality of the research data to be evaluated and verified. Essential documents are those documents that individually and collectively permit evaluation of the study and quality of the data produced. All essential documents must be stored by the Investigator, in such a way that ensures that they are readily available upon request, for the period required by ICH GCP guidelines and national legislation (whichever is longer) or for a longer period if needed. The medical files of trial subjects must be retained in accordance with applicable national legislation and the host institution policy. Generally archiving of essential documents is planned for 15 years after the trial was completed if not specified otherwise. Retention and storage of laboratory records for clinical trial samples must also follow these guidelines. It is the responsibility of the Sponsor to inform the study site when these documents no longer need to be retained. The Investigator must contact the Sponsor before destroying any study-related documentation.

Retention and storage of central laboratory records supporting PK or pharmacodynamic endpoints and the disposition of samples donated via the trial must also comply with applicable legislation and Sponsor requirements.

The Sponsor will retain ownership of all data arising from the trial. The Sponsor must review and approve any results of the study or abstracts for professional meetings prepared by the Investigator(s). Published data must not compromise the objectives of the study. Data from individual study sites in multicenter studies must not be published separately.

17 APPENDICES

17.1 Group A (Cutaneous) Schedule of Assessments Extended Treatment Period

Trial Visits, Investigations and Interventions	Treatment Period								End-of-Treatment Visit	Follow up Visit
	Week 9 ^k		Week 10		Week 11		Week 12		Week 13	Week 17
	Inj 9	Inj 10	Inj 11	Inj 12	Inj 13	Inj 14	Inj 15	Inj 16		30 days after last injection (±7 days)
RGT100 injection	+	+	+	+	+	+	+	+		
Pregnancy Test ^a	+								+	
Electrocardiogram	+								+	
Physical Examination	+		+		+		+		+	+
ECOG Performance Status	+		+		+		+		+	+
Vital Signs ^b	+++	+++	+++	+++	+++	+++	+++	+++	+	+
Overnight observation	As deemed appropriate by the investigator									
Hematology ^c	+		+		+		+		+	+
Clinical Chemistry ^c	+		+		+		+		+	+
Urinalysis ^c	+		+		+		+		+	+
Autoimmunity ^d									+	
Infectious Diseases ^c									+	
Immunoglobulins ^f									+	
Immuno-monitoring ^g									+	
Tumor Assessment ^h	+		+		+		+		+	+
Imaging ⁱ										+
Biopsy ^j									(+)	
Adverse Events	+	+	+	+	+	+	+	+	+	+
Concomitant Medication	+	+	+	+	+	+	+	+	+	+

Abbreviations: ECOG = Eastern Cooperative Oncology Group

- Mandatory for women of child bearing potential (urinary screen)
- Blood pressure, pulse rate, temperature, respiratory rate, oxygen saturation; immediately before injection and hourly up to 2 hours after each injection.
- Hematology, clinical chemistry, and urinalysis (see [Section 10.4.6.1](#) for specific parameters). Before injection.

- d. ANA, TSH, anti-thyroglobulin, rheumatoid factor, anti-smooth muscle antibodies
- e. HIV, HBV, HCV
- f. IgG, IgA, IgM, IgE
- g. Immuno-monitoring: Cytokines and exploratory samples
- h. Number of lesions (weekly), measurement of cutaneous lesions via caliper, photography of lesions every other week
- i. CT/MRI/PET-Scan to document tumor burden according to irRECIST; imaging can take place up to 7 days before follow-up visits.
- j. Biopsy (preferred excision biopsy) is optional.
- k. Can be week 9 or after the next follow up at the discretion of the investigator

17.2 Group B (Liver Tumors) Schedule of Assessments Extended Treatment Period

Trial Visits, Investigations and Interventions	Treatment Period				End-of-Treatment Visit	Follow up Visit
	Week 9 ⁱ	Week 10	Week 11	Week 12	Week 13	Week 17
	Inj 5	Inj 6	Inj 7	Inj 8		30 days after last injection (±7 days)
RGT100 injection	+	+	+	+		
Pregnancy Test ^a	+				+	
Electrocardiogram					+	
Physical Examination	+	+	+	+	+	+
ECOG Performance Status	+	+	+	+	+	+
Vital Signs ^b	+++	+++	+++	+++	+	+
Overnight observation	As deemed appropriate by the investigator					
Hematology ^c	+	+	+	+	+	+
Clinical Chemistry ^c	+	+	+	+	+	+
Urinalysis ^c	+	+	+	+	+	+
Autoimmunity ^d					+	
Infectious Diseases ^e					+	
Immunoglobulins ^f					+	
Immuno-monitoring ^g					+	
Imaging ^h						+
Biopsy					(+)	
Adverse Events	+	+	+	+	+	+
Concomitant Medication	+	+	+	+	+	+

Abbreviations: ECOG = Eastern Cooperative Oncology Group

- Mandatory for women of child bearing potential (urinary screen)
- Blood pressure, pulse rate, temperature, respiratory rate, oxygen saturation; immediately before injection and hourly up to 2 hours after each injection.
- Hematology, clinical chemistry, and urinalysis (see [Section 10.4.6.1](#) for specific parameters). Before injection.
- ANA, TSH, anti-thyroglobulin, rheumatoid factor, anti-smooth muscle antibodies
- HIV, HBV, HCV
- IgG, IgA, IgM, IgE
- Immuno-monitoring: Cytokines and exploratory samples

- h. CT/MRI/PET-Scan to document tumor burden according to irRECIST in Solid Tumors; imaging can take place up to 7 days before follow-up visits.
- i. Can be week 9 or after the next follow up.

17.3 ECOG Performance Scale

Activity Performance Description	Score
Fully active, able to carry on all pre-disease performance without restriction.	0
Restricted in physically strenuous activity but ambulatory and able to carry out work of a light or sedentary nature (e.g., light housework, office work).	1
Ambulatory and capable of all self-care, but unable to carry out any work activities. Up and about more than 50% of waking hours.	2
Capable of only limited self-care. Confined to bed or chair more than 50% of waking hours.	3
Completely disabled. Cannot carry out any self-care. Totally confined to bed or chair.	4
Death	5

17.4 Measurement of Disease – irRECIST

Objective tumor response and time of progression will be measured according to the adapted irRECIST. In 2009, immune-related response criteria⁶ were composed when RECIST⁷ were found not to provide a complete assessment of immunotherapeutic agents.

Immunotherapeutic agents produce anti-tumor effects very different from the ones caused by cytotoxic agents. In 2014, immune-related response criteria and RECIST were combined to form the irRECIST and presented at ESMO10⁸.

The following paragraphs are a quick reference to the irRECIST. The complete criteria were published online and can be reached through the following link:

https://www.parexel.com/files/7214/2313/4150/Adaptation_of_the_Immune_Related_Response_Criteria_irRECIST_online.pdf

Baseline:

Measurable Lesion Definition and Target Lesion Selection

- Follow the definitions from RECIST 1.1.
- Up to 5 target lesions may be selected at baseline.
- Measurable lesions must be accurately measured in at least 1 dimension with a minimum size of:
 - 10 mm in the longest diameter by CT or MRI scan (or no less than double the slice thickness) for non-nodal lesions and ≥ 15 mm in short axis for nodal lesions.
 - 10 mm caliper measurement by clinical exam.
 - 20 mm by chest X-ray.
 - Regardless of the imaging modality blastic bone lesions will not be selected as target lesions. Lytic or mixed lytic-blastic lesions with a measurable soft tissue component ≥ 10 mm can be selected as target lesions.
 - Brain lesions detected on brain scans can be considered as both target or non-target lesions.
 - Lesions that are partially cystic or necrotic can be selected as target lesions. The longest diameter of such a lesion will be added to the total measured tumor burden (TMTB) of all target lesions at baseline. If other lesions with a non-liquid/non-necrotic component are present, those should be preferred.
 - During target lesion selection the radiologist will consider information on the anatomical sites of previous intervention (e.g., previous irradiation, RF-ablation, transcatheter arterial chemoembolization, surgery). Lesions undergoing prior intervention will not be selected as target lesions unless there has been a demonstration of progress in the lesion.

Non-target Lesions

- Follow the definitions from RECIST 1.1.
- There is no limit to the number of non-target lesions that can be recorded at baseline.
- Non-target lesions will include:
 - Measurable lesions not selected as target lesions.

- All sites of non-measurable disease, such as neoplastic masses that are too small to measure because their longest uninterrupted diameter is < 10 mm (or < 2 times the axial slice thickness).
 - The longest perpendicular diameter is ≥ 10 mm and < 15 mm.
- Other types of lesions that are confidently felt to represent neoplastic tissue, but are difficult to measure in a reproducible manner. These include bone metastases, leptomeningeal metastases, malignant ascites, pleural or pericardial effusions, ascites, inflammatory breast disease, lymphangitis cutis/pulmonis, cystic lesions, ill-defined abdominal masses, skin lesions, etc.

Response evaluation:

Recording of Target and New Measureable Lesion Measurements

The longest diameters of non-nodal target and new non-nodal measurable lesions, and short axes of nodal target and new nodal measurable lesions will be recorded. Together they determine the TMTB at follow-up.

Definition of Measurable New Lesions

In order to be selected as new measurable lesions (≤ 2 lesions per organ, ≤ 5 lesions total, per timepoint), new lesions must meet criteria as defined for baseline target lesion selection and meet the same minimum size requirements of 10 mm in long diameter and minimum 15 mm in short axis for new measurable lymph nodes. New measurable lesions shall be prioritized according to size, and the largest lesions shall be selected as new measured lesions.

Non-Target Lesion Assessment

The RECIST 1.1 definitions for the assessment of non-target lesions apply. The response of non-target lesions primarily contributes to the overall response assessments of irCR and irNon-CR/Non-PD (irNN). Non-target lesions do not affect irPR and irSD assessments. Only a massive and unequivocal worsening of non-target lesions alone, even without progress in the TMTB is indicative of irPD.

All new lesions not selected as new measurable lesions are considered new non-measurable lesions and are followed qualitatively. Only a massive and unequivocal progression of new non-measurable lesions leads to an overall assessment of irPD for the timepoint. Persisting new non-measurable lesions prevent irCR.

irRECIST Overall Assessments

irCR: complete disappearance of all measurable and non-measurable lesions. Lymph nodes must decrease to < 10 mm in short axis. Confirmation of response is not mandatory.

irPR: decrease of $\geq 30\%$ in TMTB relative to baseline, non-target lesions are irNN, and no unequivocal progression of new non-measurable lesions.

irSD: failure to meet criteria for irCR or irPR in the absence of irPD.

irNN: no target disease was identified at baseline and at follow-up the subject fails to meet criteria for irCR or irPD.

irPD: minimum 20% increase and minimum 5 mm absolute increase in TMTB compared to nadir, or irPD for non-target or new non-measurable lesions. Confirmation of progression is recommended minimum 4 weeks after the first irPD assessment.

irNE: used in exceptional cases where insufficient data exists.

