8.3.2 Inclusion Criteria

A subject will be eligible for inclusion in this study if all of the following criteria apply:

1. Male or female aged ≥ 18 years

2. Subjects with histologically or cytologically confirmed diagnosis of advanced or recurrent tumors (including lymphomas) for whom all standard treatments have been used or are not feasible or RGT100-PEI is a suitable treatment option and:
 - a. For Group A: has cutaneous, SC, or lymph node injectable tumors
 - b. For Group B: has injectable liver tumors or liver metastases
3. Eastern Cooperative Oncology Group (ECOG) performance status 0-2
4. Life expectancy > 3 months as assessed by the Investigator
5. Adequate organ function:
 - a. Bone marrow function: Hemoglobin ≥ 10 g/dL (pre-treatment transfusion allowed); lymphocyte count $\geq 0.5 \times 10^9/L$; absolute neutrophil count $\geq 0.5 \times 10^9/L$; platelet count $\geq 75 \times 10^9/L$
 - b. Hepatic function: AST and ALT $\leq 2 \times$ upper limit of normal (ULN) ($3 \times$ ULN in the case of liver metastases); bilirubin $\leq 1.5 \times$ ULN ($2 \times$ ULN in case of liver metastases)
 - c. Renal function: creatinine $< 1.5 \times$ ULN and/or creatinine clearance ≥ 50 mL/min (Cockcroft and Gault)
6. Negative serum pregnancy test within 2 weeks before first dose of study drug if the subject is a woman of childbearing potential. Subjects and subjects' partners of childbearing potential must agree to use birth control consistently and correctly during the study and for at least 6 months after the last study drug application.
7. At least 1 measurable lesion per RECIST 1.1 and 1 separate injectable lesion with diameter ≥ 1 cm but < 7 cm
8. Ability to provide written informed consent before any study drug-related screening procedures being performed

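### Appendix 17.4 gives conflicting rules for partial response: irPR requires non-target lesions to be irNN, a category it defines only for subjects without target disease, while its non-target paragraph says these lesions do not matter for irPR

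*Combined protocol and SAP*

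**What the plan says.** Four statements in Appendix 17.4 bear on the point.

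- **irPR** (Overall Assessments): TMTB must be at least 30% below baseline, and in addition "non-target lesions are irNN, and no unequivocal progression of new non-measurable lesions".
- **irNN** (Overall Assessments), the only definition given: "no target disease was identified at baseline and at follow-up the subject fails to meet criteria for irCR or irPD".
- **irSD** (Overall Assessments), the default category: "irSD: failure to meet criteria for irCR or irPR in the absence of irPD".
- **Non-Target Lesion Assessment**: irNN is spelled out as irNon-CR/Non-PD, an assessment to which the non-target response contributes. The paragraph then states: "Non-target lesions do not affect irPR and irSD assessments". Only massive, unequivocal worsening of non-target lesions leads to irPD.

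Elsewhere, Section 8.3.2 (criterion 7) requires "At least 1 measurable lesion per RECIST 1.1 and 1 separate injectable lesion". Section 7.2 names objective response rate by irRECIST as the single secondary endpoint. Section 11.1.4.1 defines it as CR or PR, with Clopper–Pearson intervals, and computes duration of response in responders only.

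**The concern.** One term, irNN, is used in two ways: as a status of the non-target lesions (in the irPR line and, by its expansion, in the non-target paragraph) and as an overall category for a subject. The appendix defines only the second. Separately, the irPR line gives non-target lesions a role that the non-target paragraph denies them.

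At stake is the boundary between irPR and irSD, which decides who counts as a responder. That feeds the response rate, duration of response and the regressions on overall response (Section 11.1.4.2). It may also feed the choice of expansion tumor types, which Section 8.3.1 bases on preliminary anti-tumor activity.

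The affected pattern is plausible here. Section 8.4.1.1 has the non-injected lesions for irRECIST follow-up fixed at screening and foresees that an injected lesion may disappear during treatment. A measurable injected lesion not chosen as a target is a non-target lesion under Appendix 17.4. If it disappears while an uninjected target lesion shrinks by 30% or more without vanishing, the rules disagree on the result.

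**Working it through.** The plan states no figure that depends on this definition, and Section 11.2.2 reports no power calculation, so there is nothing to reproduce. The check is a logic table, followed by the weight of one subject.

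**Step 1. Can the irPR line and the irNN definition both be met?** irPR needs a fall in TMTB from baseline, which presupposes target lesions at baseline. irNN as defined needs their absence. No subject satisfies both. Criterion 7 also means that target disease is expected in every eligible subject.

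**Step 2. Score one subject under each reading.** Take a subject with target disease at baseline, TMTB down by at least 30%, some target disease left (so not irCR), and no progression of new lesions.

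- Reading A: irNN exactly as defined.
- Reading B: irNN means non-target status non-CR/non-PD.
- Reading C: the non-target paragraph governs, so non-target lesions matter only through irPD.

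| Non-target lesions | A | B | C |
|---|---|---|---|
| None at baseline | irSD | irSD, or irPR if the condition is treated as not applicable | irPR |
| All disappeared | irSD | irSD | irPR |
| Present, non-CR/non-PD | irSD | irPR | irPR |
| irPD | irPD | irPD | irPD |

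The irSD entries follow from the default in the irSD line. Under A, irPR is never reached. Under B, the subject whose non-target lesions have all gone ranks below the subject whose non-target lesions persist. Under C neither problem arises, but the irNN condition in the irPR line then has no effect.

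**Step 3. Weight of one reclassified subject.** The change in response rate is 1/n.

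- Cohort of 6 (the most evaluable subjects at one dose level in Table 1): 1/6 = 16.7 points.
- Expansion group of 15 (Section 11.2.2): 1/15 = 6.7 points.

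For x responders among n, the Clopper–Pearson limits are the 0.025 quantile of Beta(x, n−x+1) and the 0.975 quantile of Beta(x+1, n−x). The lower limit is 0 when x = 0. With n = 15:

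| Scored irSD | Scored irPR |
|---|---|
| 0/15 = 0% (0 to 21.8) | 1/15 = 6.7% (0.2 to 31.9) |
| 2/15 = 13.3% (1.7 to 40.5) | 3/15 = 20.0% (4.3 to 48.1) |

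These are the effects of a single subject. They do not estimate how often the pattern occurs.

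**The case against.** The strongest reply is that the appendix already contains the sensible rule. The non-target paragraph gives irNN its ordinary meaning and keeps non-target lesions out of irPR, so an assessor who follows it scores the subject as irPR. The appendix also says "The following paragraphs are a quick reference to the irRECIST" and links the complete criteria, and Section 10.1.1.2 asks radiologists to work in accordance with irRECIST. For a subject with no non-target lesions, a condition on those lesions can be taken as trivially met. Finally, the response rate is descriptive, and the expansion phase is not meant to be definitive.

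Much of this stands as a limit on the point. A reader might infer that partial response is unattainable in this trial, or that every responder with resolved or absent non-target disease will be misclassified and the response rate biased downward. The documents do not support that. It requires every assessor to apply the irPR line literally, or to read irNN as non-CR/non-PD, and to set the non-target sentence aside.

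The contradiction itself is not removed. The appendix does not say which of its sentences prevails, nor that the linked criteria override it. Section 10.1.1 presents the appendix as the summary to be used, though it cites 17.3, which is the ECOG scale. The linked criteria were not available, so nothing is claimed about what they say.

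**Conclusion.** Wrong as written. The irPR line, the irNN definition and the non-target paragraph cannot all be applied, and for a subject with a sufficient TMTB fall, residual target disease and complete non-target disappearance they give irSD or irPR depending on which is followed. The case with no non-target lesions is arguable in the same way.

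Each affected subject is worth 16.7 points of response rate in a cohort of 6 and 6.7 points in 15. The documents give no basis for how many there would be. If all assessors follow the non-target paragraph, nobody is misclassified; if they differ, classification varies by assessor.

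The consequence is confined to labelling irPR against irSD in the response rate, duration of response and analyses built on them. Escalation under Table 1 rests on DLTs, and PR and SD are treated alike at Week 8 (Synopsis, Section 8.1.3). One indirect route remains: if no MTD is reached, Section 8.4.8 lets clinical benefit contribute to the RP2D.

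**What to change.** Reword three places in Appendix 17.4.

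1. **irPR**: TMTB at least 30% below its baseline value; non-target lesions not irPD, meaning absent, resolved or non-CR/non-PD; and the existing condition on new non-measurable lesions kept.
2. **irNN**: use one term for the non-target lesion status (non-CR/non-PD) and another for the overall category of a subject with no target disease at baseline.
3. **Non-Target Lesion Assessment**: reword the sentence on irPR and irSD so that it agrees, saying that non-target lesions affect these categories only through irPD.

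It would help to add which text prevails if the appendix and the linked criteria differ, and to correct the cross-reference in Section 10.1.1.

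The cost is appendix wording. No visit, measurement or sample size changes. Section 8.1.2 already requires an amendment before expansion, which is the latest natural point for the change. Escalation responses are scored by the same appendix, so an earlier correction is preferable, with any responses already assigned checked against the revised rule.
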